3.1 PRIMARY ESTIMAND

The primary question of scientific interest is “Does administration of RO7049665 to participants with confirmed AIH and in stable biochemical remission ≥ 2 years (*or less if according to local clinical practice*) and on stable immunosuppressive treatment ≥ 3 months *prior to randomization (and no dose increase within the previous 6 months prior to randomization)* affect the time to relapse following forced CCS tapering?” The following sections describe the components of the corresponding estimand.

For details on the study population, see Section 5.

3.1.1 Treatment

The treatment of interest is treatment with RO7049665. Each dose of RO7049665 used in this study will be analyzed separately. Use of prohibited concomitant medications and missed doses will be regarded as intercurrent events and will be handled in ways described in Section 3.1.3.

3.1.2 Endpoint

The patient-level endpoint that provides information about the question of scientific interest is the number of days from randomization to relapse. A participant will be considered to have relapsed the first time they meet the criteria given in Section 8.1 at a

post-baseline study visit, whether the visit is scheduled or unscheduled. If the relapse requires confirmation at a subsequent visit, the date of relapse will be the date of the first set of tests, if confirmed. The sensitivity analyses below will examine the effect of how missing confirmatory tests are handled and the impacts on the results of the trial.

3.1.3 Intercurrent Events

The following intercurrent events will be handled using a treatment policy strategy. That is, the primary endpoint will be defined to be the earliest of the time to relapse as described in Section 8.1 and the time at which any of the events defined below occur.

Table 6 Intercurrent Events and the Statistical Treatment

Permanent discontinuation of study medication unrelated to treatment.	Censored
Permanent discontinuation of study medication related to treatment.	Estimand event
Temporary discontinuation of study medication regardless of relationship to treatment will be discussed by the Sponsor and the Investigator to determine whether patient can stay in the study and restart treatment (see Section 7.1.1).	In case of permanent discontinuation, see rows 1 and 2.
Initiation of treatment with any systemic CCSs (not related to AIH), or any other prohibited concomitant medication listed in Section 6.5.2.	Censored
Death due to any cause.	Censored
Liver transplant.	Censored
CCS increase during tapering or reintroduction related to AIH.	Estimand event

In the primary analysis of the primary estimand, participants who experience any of these intercurrent events will have a response status as indicated in Table 6 at the time of their earliest intercurrent event. Other strategies will be adopted in sensitivity analyses (see Section 3.1.5).

Participants who neither relapse nor experience any of the intercurrent events will be regarded as censored on the date of their last known follow-up.

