3.1.5 Sensitivity Analyses

The most likely cause of “missing” confirmation of relapse is the absence of a confirmatory laboratory test results. Therefore, the first sensitivity analysis will define relapse to have occurred on the date of the tests that triggered the need for a subsequent confirmation, regardless of the result of that confirmation. The status of participants whose laboratory test results indicate definitive relapse without the need for confirmation will be unchanged. Moreover, if exactly one of the values for ALT or IgG is missing at a given visit, this analysis will assume that the missing test meets the criterion for retest, and therefore that the participant will have relapsed at that visit.

Additional sensitivity analyses will regard all intercurrent events listed above as relapses rather than as censorings and regard all intercurrent events listed above as censorings rather than as events.

The fourth and final sensitivity analysis will use multiple imputation to replace any missing laboratory test result with values selected at random from other participants in the study, matched for sex and prednisolone-equivalent CCS dose. Further details of the methodology used will be documented in the study electronic Trial Master File (eTMF).

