4. STUDY DESIGN

4.1 OVERALL DESIGN

An overview of the study design is provided in Section [1.2](#).

Study BP42698 is a 3-parallel arm (two dose levels of RO7049665 versus placebo), randomized, placebo-controlled, double-blind, event-driven, phase 2 study to assess efficacy of RO7049665 over placebo in patients with AIH in stable biochemical remission.

Two dose levels will be assessed, 3.5 mg RO7049665 (SC, Q2W) and 7.5 mg RO7049665 (SC, Q2W) and matching placebo.

This is an event-driven study, which means that participants stay in the study and on treatment until the participant experiences an event, the necessary number of events is reached, the participant stops for other reasons or withdraws consent, or the study ends.

All participants in the study will have been diagnosed with AIH previously and will have responded well to treatment with CCSs \pm NSIs. It will be the first attempt to taper out CCS completely *within the last 3 years* (see inclusion criteria Section [5.1](#)). At study entry, the disease status of the participants should allow for a stepwise removal of all

immunosuppressive treatment according to *local guidelines or practice*. If no local guidelines exist, EASL guidelines should be applied (EASL 2015: “Treatment should be continued for at least three years and for at least 24 months after complete normalisation of serum transaminases and IgG levels (biochemical remission). [...] In patients with continued histological disease activity (HAI >3), immunosuppressive treatment should not be discontinued, as relapse is almost certain to occur. [...] A trial of treatment withdrawal should be undertaken by stepwise reduction of immunosuppressive agents, and patients monitored closely.”). Participants will start with study treatment on Day 1 and start tapering CCS use from Day 8 onwards (see tapering schedule, Section 1.3, Table 3) to allow for complete CCS withdrawal within a maximum of 12 weeks, depending on the starting dose. Last dose of NSIs, if any, will be taken on Day –1.

Randomization in a 1:1:1 fashion will occur after patient eligibility is confirmed and before the first dose of study treatment is administered. Randomization will be stratified by equivalent prednisolone dose (≤ 7.5 mg daily versus > 7.5 mg daily or dual therapy [CCS any dose, plus NSI]).

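### Section 3.1.3 calls its handling of intercurrent events treatment policy, which fits only one row of Table 6, and row 4 censors a prohibited non-CCS drug even when it is started for an AIH flare

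*Combined protocol and SAP*

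**What the plan says.** All references are to the combined protocol and SAP.

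- **Label (3.1.3).** "The following intercurrent events will be handled using a treatment policy strategy". The next sentence takes the endpoint as the earlier of relapse and any listed event. A later paragraph says that participants with such an event "will have a response status as indicated in Table 6 at the time of their earliest intercurrent event".
- **Table 6.** Of its seven rows, two are Estimand events: permanent discontinuation related to treatment (row 2), and "CCS increase during tapering or reintroduction related to AIH" (row 7). Four are censored: unrelated permanent discontinuation (row 1), prohibited medication (row 4), death (row 5) and liver transplant (row 6). Row 3, temporary discontinuation, sets no status unless discontinuation becomes permanent.
- **Row 4.** "Initiation of treatment with any systemic CCSs (not related to AIH), or any other prohibited concomitant medication listed in Section 6.5.2": censored.
- **Prohibited therapy (6.5.2).** A general rule allows no drug for the underlying disease apart from CCS during the taper. Two bullets follow: CCS after the taper, and other immune-targeted biologics. NSIs are in neither bullet.
- **Treatment (3.1.1).** "Use of prohibited concomitant medications and missed doses will be regarded as intercurrent events".
- **Efficacy assessments (8.1).** CCS increased or restarted for an AIH flare, in the investigator's judgment, counts as an event. Only CCS is named.

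**The concern.** A treatment policy strategy keeps following the participant and counts later relapses. A reader who trusts the label will expect that for every row, and Table 6 does it for one.

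The coding matters more than the name. Starting rescue for a flare is evidence of treatment failure. If one drug class makes it an event and another makes it a censoring, the primary analysis censors informatively for the second class. The hazard ratio could then move in either direction, and the 6-month relapse rates reported under 9.5.2.1 would be slightly too low.

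NSIs deserve a stated status because some participants enter on dual therapy. Section 4.1 says: "Last dose of NSIs, if any, will be taken on Day" −1. Restarting the drug is therefore a case the coding should cover.

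**Working it through.** **Step 1. Label against rows.** Rows 2 and 7 are composite. Rows 1, 4, 5 and 6 are censoring, that is, a hypothetical strategy. Row 3 is treatment policy in substance: 7.1.1 allows dosing to resume and assessments continue where possible, so later relapses count. The label fits one row of seven.

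**Step 2. One sub-threshold flare, three first treatments.** Section 8.1 itself gives prolonged ALT between 1 and 2, or a biopsy finding, as examples of such a flare.

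| First drug started for AIH | Status | Source |
|---|---|---|
| CCS | Event | Table 6 row 7; 8.1 |
| Biologic | Censored | Row 4 with the 6.5.2 bullet |
| NSI, if the general rule counts as listed | Censored | Row 4 with the 6.5.2 general rule; 3.1.1 points this way |
| NSI, if only the bullets count | No intercurrent event; follow-up continues | 6.5.2 bullets |

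In row 4 the AIH qualifier follows systemic CCSs only. If it were read across the whole row, a biologic for AIH would have no row, and would still not be an event.

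**Step 3. Which cases are exposed.** A confirmed relapse is safe: "the date of relapse will be the date of the first set of tests, if confirmed", so it precedes later rescue. A flare that crossed a threshold and was treated while awaiting confirmation is recovered by the first analysis in 3.1.5, which dates relapse at the triggering test "regardless of the result of that confirmation". What remains is mainly a flare that never crossed a threshold and was treated first with a non-CCS drug.

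**Step 4. The plan's own figures.** From 9.1, under exponential times:
- placebo hazard −ln(0.55)/6, mean 10.04 months (stated 10.0);
- active hazard −ln(0.85)/6, mean 36.92 months (stated 36.9);
- HR 0.2718 (stated 0.272).

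Rebuilding the group sequential design of 9.2 gives 29.09 events (stated 29.1). The final boundary is exp(−2 × 1.969/√29.1) = 0.482, as in Table 9.

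**Step 5. Effect of one participant.** This is a unit effect, not a predicted rate. Expected 6-month failures with 28 per arm are 28 × 0.45 = 12.6 on placebo and 28 × 0.15 = 4.2 on 7.5 mg. Scaling the hazard for one failure recoded as censored:
- placebo: 1 − 0.55^(1 − 1/12.6) = 42.3% instead of 45%;
- active: 1 − 0.85^(1 − 1/4.2) = 11.6% instead of 15%.

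For the HR, 4,000 trials were simulated per scenario. Assumptions: 28 per arm in three arms, accrual rising for 6 months and then flat to month 19, no dropout, cut at the 45th event in the whole study (9.6), and an unadjusted Cox model of 7.5 mg against placebo. One random event was recoded as censored at its own time; the median change in log HR was applied to 0.272.

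| Assumption for 3.5 mg | One placebo case | One active case |
|---|---|---|
| Acts like 7.5 mg | × 1.043 = 0.284 | × 0.907 = 0.247 |
| Inert | × 1.055 = 0.287 | × 0.868 = 0.236 |

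**Step 6. An equal share in both arms.** If 5% of failures in each arm were censored (an assumption), the 6-month rates would be 1 − 0.55^0.95 = 43.3% and 1 − 0.85^0.95 = 14.3%, with the HR unchanged.

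**The case against.** The best case for leaving the text alone is that the exposed participant is hypothetical. Section 6.5.2 permits no such treatment, 6.5 places NSIs after relapse, 8.1 gives CCS as the response to a sub-threshold flare, and waivers are not allowed. Section 3.1.5 also plans an analysis that turns every listed intercurrent event into a relapse, which recodes row 4 in full.

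Most of this stands and limits the size. It does not remove the inconsistency, because row 4 exists to code prohibited medication. The all-as-relapse analysis is only a partial bound: it also turns deaths, transplants and non-AIH CCS use into relapses, so it does not isolate AIH rescue. It misses an NSI that is not counted as listed.

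Four stronger readings are tempting and are not supported:

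- **That no row follows treatment policy.** Row 3 does.
- **That the sentence taking the earlier of relapse and any listed event contradicts Table 6.** It can be read as setting the time, with Table 6 setting the status.
- **That same-day CCS plus NSI for one flare cannot be resolved.** Table 6 has no tie rule, but 8.1 counts AIH-related CCS as an event and 3.1.2 defines relapse by 8.1, so there is a basis for calling it an event.
- **That the primary test is materially biased.** One can construct this. If 10% of flares were censored in the active arm only, with no true effect, one-sided type I error would be 4.7% instead of 2.5% (futility ignored). If 10% were censored on placebo only, the HR would be 0.302 and power 85%. The documents give neither such a share nor a reason to expect an imbalance between arms.

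**Conclusion.** The point holds and is minor. The strategy label is wrong for six of seven rows. Row 4 as written gives a biologic started for an AIH flare a different status from CCS for the same flare, and the status of an NSI started for AIH depends on how 6.5.2 is read.

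The effect on the HR is unknown and probably small, and its direction cannot be predicted. One affected participant would leave the HR well below 0.482 if the design assumptions hold. That statement rests on the exponential rates in 9.1, 28 per arm, no dropout and the accrual pattern assumed above. It says nothing about how often such a case occurs. The case for acting is that the rule belongs to the primary endpoint, is cheap to settle now, and would be open to challenge if clarified after unblinded results exist.

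**What to change.** For event coding only:

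1. In 3.1.3, replace the single label by one per row: composite where Table 6 says Estimand event, hypothetical (censoring) where it says Censored, treatment policy for temporary discontinuation. State that the earliest-time sentence sets the time and Table 6 sets the status.
2. Limit row 4 to prohibited medication not given for AIH. Extend the last row so that starting any other systemic immunosuppressive or biologic therapy for AIH, including an NSI, is an Estimand event. State that an event takes precedence over a censoring on the same day, consistent with 8.1.
3. In 8.1, add a cross-reference to Table 6 for coding. Change no treatment, prohibited-therapy or stopping rule. The stopping text in 8.1 names only CCS, so the sponsor must reconcile it with the wider event row.
4. Fix the rule before the first unblinded interim analysis, and classify reason for use blind to arm at each data cut (12, 23 and 45 events).

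The cost is wording in 3.1.3 and Table 6, one cross-reference, and a small blinded classification task at each cut. Section 6.5.1 already requires reason for use and dates to be recorded. The event target and boundaries are unchanged.

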2.3 BENEFIT/RISK ASSESSMENT

As mentioned in Section 2.2.1, AIH is a chronic autoimmune disease of unknown cause, characterized by continuing hepatocellular inflammation and necrosis; it has a tendency to progress to cirrhosis. Some patients go on to develop signs and symptoms of chronic liver disease, while others rapidly progress to acute liver failure, as marked by coagulopathy and jaundice ([Wolf DC, 2019](#)). There is no registered treatment for AIH. SoC is CCS, possibly with the addition of NSIs such as, but not limited to, azathioprine (AZA), 6-mercaptopurine (6-MP) mycophenolate-mofetil (MMF) methotrexate, cyclosporine, or tacrolimus. While the vast majority of patients are responsive to CCSs, 80% of patients relapse when the CCS and /or immunosuppressive treatment is withdrawn ([van Gerven NM et al. 2013](#)). Untreated AIH has a high mortality rate due to the development of liver cirrhosis. Thus, most patients with AIH require lifelong CCS and/or immunosuppressant treatment and suffer from the side effects of chronic treatment, including osteoporosis (particularly worrisome, as AIH is common in young women), skin effects, depression, diabetes and metabolic syndrome, infection risk, etc.

The hallmark laboratory findings in AIH are elevated liver enzymes (notably ALT) and elevated serum Ig levels, primarily IgG. ALT and IgG are also the recognized disease activity markers, and the treatment goal is normalization of these two markers (known as "biochemical remission"). In most patients, this can be achieved quickly by induction of high-dose CCS therapy followed by the addition of NSIs. After response to induction therapy, CCS dose is reduced in a stepwise fashion. Complete withdrawal of immunosuppressive therapy is tried after approximately 2 years of stable remission ([EASL, 2015](#)). However, it is rarely successful; > 80% of patients require re-instigation of CCS treatment ([van Gerven NM et al. 2013](#)). Patients who relapse twice usually need to stay on immunosuppressive treatment for the rest of their life ([EASL, 2015](#)).

RO7049665 represents a potential novel therapy for AIH aiming at long-term, CCS-free remission.

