7. DEATHS

All deaths that occur during the protocol-specified adverse event reporting period (see Section 5 of [Appendix 2](#)), regardless of relationship to study treatment, must be recorded on the Adverse Event eCRF and immediately reported to the Sponsor. This includes death attributed to progression of autoimmune hepatitis.

Death should be considered an outcome and not a distinct event. The event or condition that caused or contributed to the fatal outcome should be recorded as the single medical concept on the Adverse Event eCRF. Generally, only one such event should be reported. If the cause of death is unknown and cannot be ascertained at the time of reporting, "unexplained death" should be recorded on the Adverse Event eCRF. If the cause of death later becomes available (e.g., after autopsy), "unexplained death" should be replaced by the established cause of death. The term "sudden death" should not be used unless combined with the presumed cause of death (e.g., "sudden cardiac death").

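### Table 6 censors death and liver transplant of any cause when they come first, although milder outcomes of the same cause are events, and it conflicts with the Section 3.1.3 lead-in

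*Combined protocol and SAP*

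**What the plan says.** Section 3.1.3, Table 6 assigns a status to each intercurrent event.

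- Censored: "Death due to any cause" (row 5); "Liver transplant" (row 6); "Initiation of treatment with any systemic CCSs (not related to AIH), or any other prohibited concomitant medication listed in Section 6.5.2" (row 4); and permanent discontinuation unrelated to treatment (row 1).
- Estimand event: "Permanent discontinuation of study medication related to treatment" (row 2) and "CCS increase during tapering or reintroduction related to AIH" (row 7).

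Rows 5 and 6 are not split by cause or indication. The paragraph after the table makes these statuses binding: affected participants "will have a response status as indicated in Table 6 at the time of their earliest intercurrent event".

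The lead-in says something else. It names a treatment policy strategy and defines the endpoint as whichever comes first, relapse under Section 8.1 or any of the listed occurrences. Section 3.1.5 adds sensitivity analyses. One dates relapse at the triggering test whatever the confirmation shows, one treats all intercurrent events as relapses, and one treats all of them as censorings.

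**The concern.** The trial withdraws all immunosuppression and asks whether the drug delays failure. Within a single causal chain, Table 6 reverses the order of severity. A steroid increase for an AIH flare is a failure, but death or transplant from the same flare, if nothing countable preceded it, is not. A drug reaction that ends dosing is a failure, while a fatal one falls under a censoring row as well.

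A Cox model fitted with these rows treats such a participant as leaving the risk set without failing. For an AIH death or a transplant for AIH, that removes a treatment failure from the arm in which it happened, so the comparison shifts in that arm's favour. Because the lead-in and the table disagree, two analysts could also code the same case differently.

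**Working it through.** **1. Table 6 against its lead-in.** Under the lead-in, death and transplant end the time-to-event clock as events. Under rows 5 and 6 they are censored. The treatment policy label fits neither, because that strategy uses the relapse time regardless of the intercurrent event. The sentence after the table settles the primary analysis in favour of the table.

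**2. When the rule bites.** It applies only if death or transplant is the first event. Two routes remain open.
- A rapid flare ends in death or transplant before any Table 8 sample is drawn.
- A confirmatory test is pending. Table 8 requires confirmation at +7 days, and possibly 7 more, for ALT from 2 to below 5 x ULN. It requires +14 days, and possibly 14 more, for IgG above 1 and below 1.5 x ULN. Section 3.1.2 dates relapse to the first test only if it is confirmed.

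**3. Fatal treatment-related reaction.** Dosing ends permanently and for a related reason, so row 2 gives an event. The participant has died, so row 5 gives censoring. If both fall on the same date, the earliest-event rule does not choose between them.

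**4. The plan's own figures.** Hazards from Section 9.1 are:
- placebo: -ln(0.55)/6 = 0.0996 per month
- 7.5 mg: -ln(0.85)/6 = 0.0271 per month
- ratio: 0.272, as stated

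Recomputing the group sequential design by numerical integration (O'Brien-Fleming-type alpha spending, Pocock-type beta spending, non-binding futility) gives 29.09 events against the stated 29.1. The design has no input for deaths or transplants, so this figure does not depend on how they are coded.

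**5. Expected events per arm at month 25.** I assumed that accrual rises linearly over 6 months and is then flat to month 19. The accrual weight is a(s) = s/6 for s < 6 and 1 thereafter, which totals 3 + 13 = 16. This puts 56 x 8.7/16 = 30.45 participants in two arms at 11.7 months and 56 x 13.3/16 = 46.55 at 16.3 months. Table 9 shows 31 and 47.

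Events = 28 x (1/16) x integral from 0 to 19 of a(s)[1 - exp(-hazard x (25 - s))] ds
- placebo: 20.33
- 7.5 mg: 8.73
- sum: 29.06, against 29.1 in Table 9

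**6. Effect of recoding one case from censored to event.** With exponential times, the hazard ratio is a ratio of events per unit of exposure. Recoding leaves exposure unchanged.
- On 7.5 mg: 9.73/8.73 = 1.11, so 0.272 becomes 0.303.
- On placebo: 20.33/21.33 = 0.953, so 0.272 becomes 0.259.
- Standard error of the log hazard ratio: sqrt(1/8.73 + 1/20.33) = 0.405. The shifts are 0.108/0.405 = 0.27 and 0.048/0.405 = 0.12 standard errors.

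**7. Effect on the chance of success.** This is an illustration on assumptions of mine: 28 per arm, uniform 19-month entry, one final log-rank test at z > 1.969, 8,000 simulations, and k first-event deaths or transplants, all on 7.5 mg.

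| True HR | Coding | k = 0 | 1 | 2 | 3 |
|---|---|---|---|---|---|
| 0.272 | censored | 0.94 | 0.94 | 0.94 | 0.95 |
| 0.272 | event | 0.94 | 0.91 | 0.88 | 0.84 |
| 0.45 | censored | 0.64 | 0.65 | 0.66 | 0.68 |
| 0.45 | event | 0.64 | 0.58 | 0.52 | 0.46 |

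**The case against.** **Most severe cases already count.** A single ALT at or above 5 x ULN, or IgG at or above 1.5 x ULN, is relapse without confirmation (Table 8), and unscheduled visits qualify (Section 3.1.2). Steroids given for AIH are an event. A related Grade 3 or greater AE or SAE stops dosing (Section 4.1.3), and a related permanent stop is an event. This stands. A reader might infer that every AIH death, transplant or drug-related death is lost from the endpoint. The documents do not support that, because only first-event cases are affected. Nor is a fatal drug reaction simply censored; its status is undetermined.

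**The protocol does not forecast such cases.** Section 2.3 says that "others rapidly progress to acute liver failure", but this describes AIH in general. Appendix 3, Section 7 says of death reporting: "This includes death attributed to progression of autoimmune hepatitis". That is a recording rule. Participants enter in biochemical remission with HAI of 3 or less. This stands too: no expected number is given, and it may be near zero.

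**Sensitivity analyses cover the issue.** They do so in part. Treating all intercurrent events as relapses counts every death and transplant, but also unrelated stops and non-AIH steroid courses. Dating relapse at the triggering test captures the pending-confirmation route, but also counts rises that were not confirmed, and it misses a flare with no sample. Neither isolates the issue.

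**Censoring death gives a cause-specific relapse hazard, which is a legitimate quantity.** That is true for unrelated deaths. It is a weak defence for AIH deaths, which are consequences of the failure being measured. The endpoint is also already wider than relapse, since rows 2 and 7 are events.

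**Conclusion.** The point holds for death or transplant as the first event. Rows 5 and 6 code the worst AIH-related outcome as non-failure, they contradict the section's lead-in, and rows 2 and 5 collide for a fatal treatment-related reaction. This is a flaw in the estimand definition, and a reader should not take it as an error in the sample size.

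The size is modest. One recoded case moves the hazard ratio by about +11% (7.5 mg) or -5% (placebo), against a final boundary of 0.482 in Table 9. At the design effect, one case on 7.5 mg takes the chance of success from 0.94 if censored to 0.91 if counted. Larger differences need a weaker true effect or several cases in one arm. These figures rest on exponential times, the accrual shape assumed above and, for the simulation, an assumed 0 to 3 cases.

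**What to change.** In Table 6:
- Count death or liver transplant attributed to AIH/liver disease or to study treatment as an estimand event on its date.
- State that this takes precedence over the censoring rows.
- Keep other deaths censored.

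In Section 3.1.3, replace the treatment policy label and reword the lead-in so that both match the table. List all deaths and transplants by arm beside the primary result.

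The cost is two table rows and a corrected paragraph. The condition causing death is already recorded (Appendix 3, Section 7), as is Investigator causality (Appendix 2, Section 3.2). Under Appendix 2, Section 1, the condition leading to a procedure such as transplant is treated as the AE. Attribution should be fixed before unblinding, and no extra adjudication committee is needed. The small downside is that Investigator causality enters the endpoint, as it already does through rows 1 and 2.
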